10.3. Sets for Analyses

10.3.1. Enrolled Set

The Enrolled Set will include all subjects with informed consent signed.

10.3.2. Exposed Set

The Exposed Set will include all enrolled subjects who are vaccinated with GSK's quadrivalent seasonal influenza vaccine.

10.3.3. Safety Set

The Safety Set will include all subjects from the Exposed Set who received the ADR card.

10.3.4. Solicited Safety Set

The Solicited Safety Set will include all subjects from the Safety Set who returned the ADR card.

10.4. Derived and Transformed Data

Demography:

- For a given subject and a given demographic variable, missing measurements will not be imputed.
- Age at the vaccination will be computed as the difference between the vaccination date and the date of birth. The age will be expressed in years.

Safety:

- Subjects who did not report an adverse event will be considered as subjects who did not experience adverse event.

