- Epoch 001: Prospective data collection starting at Visit 1 (Day 1) and ending at Visit 2 (Day 8 or when the ADR card is returned by mail) for all subjects who have previously been vaccinated against influenza in preceding seasons or aged ≥ 9 years at the time of vaccination, or ending at Visit 4 (Day 36 or when the last ADR card is returned by mail) for children aged < 9 years who have not previously been vaccinated against influenza in preceding seasons). Subjects will have up to 14 days post vaccination to return their ADR card (at the next study visit or by mail).

Table 1 Study groups and epochs foreseen in the study

Study Groups	Number of subjects	Age (Min/Max)	Epochs
Prospective	Approximately 1000	6 months and above	Epoch 001

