4.1. Discussion of Study Design

The study is a passive enhanced safety surveillance aiming to collect prospectively AEIs and/or other AEs (see [APPENDIX C](#)) experienced within 7 days post vaccination with GSK's quadrivalent seasonal influenza vaccine, using customized Adverse Drug Reaction cards (see [APPENDIX A](#)). Data will be collected via the HCP or study medical staff who administer the seasonal influenza vaccination or who provide the *informed* consent form and the ADR cards.

After written informed consent/informed assent is obtained from the subject/subject's parent(s)/Legally Acceptable Representative (LAR), an ADR card will be distributed to the enrolled subjects/subjects' parent(s)/LAR who will be asked to complete the card and return this to the HCP (or a member of his/her team) either in person at the next scheduled visit or by mail. Upon return, the card information will be entered into a database using eCRF.

The cards will contain pre-defined AEIs to be reported as well as a free text field to report other relevant AEs experienced by the subjects. Subjects will also have the possibility to indicate that no AE occurred within the 7 days' time window.

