9. SUBJECT COMPLETION AND WITHDRAWAL

9.1. Subject Completion

A subject who returns for the concluding visit foreseen in the protocol or has returned the completed ADR card is considered to have completed the study.

9.2. *Subject Withdrawal*

A subject who does not return for the concluding visit foreseen in the protocol or has not returned the completed ADR card will be considered a withdrawal from the study. If the subject informs the Investigator of the reason for withdrawal from the study, the reason for this will be entered into the electronic Case Report Form as detailed below:

- *Seasonal influenza vaccine-related Serious Adverse Event*
- *Protocol Violation (to be specified)*
- *Consent withdrawal, not due to an adverse event (to be specified if the information is available)*
- *Not willing/not able to participate in the visit*
- *Migrated/moved from the study area*
- *Lost to follow-up*
- *Sponsor study termination*
- *Other (please specify)*

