10. STATISTICAL METHODS

10.1. Endpoints

10.1.1. Primary endpoint

- Occurrence of AEs and/or other AEs within 7 days post each GSK's quadrivalent seasonal influenza vaccination (i.e., the day of vaccination and the following 6 days) reported using ADR cards, according to MedDRA classification, by cumulative weeks (expected ISO weeks 40 to 52).

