10.6. Analysis of Primary Objective

The primary analysis of AEs and/or other AEs reported using ADR cards will be descriptive and will be performed on the Safety Set.

For each vaccine dose*, the cumulative percentage of subjects reporting AEs and/or other AEs within 7 days post-vaccination period (i.e., the day of vaccination and the following 6 days) using ADR cards from study start up to each study week (ISO weeks 40 to 52) will be estimated by MedDRA Preferred Term, overall and by country, as follows:

- The denominator will be the number of subjects *from the Safety Set* vaccinated with GSK's quadrivalent seasonal influenza vaccine at any point from study start (i.e., 01 October 2018) up to the end of the week of interest, in a given country or for all countries.
- The numerator will be the number of subjects from the denominator who reported the AE on the ADR card within 7 days following vaccination.

* Note that a second dose of GSK's quadrivalent seasonal influenza vaccine is planned to be administered only to children aged <9 years who have not previously been vaccinated against influenza in preceding seasons.

95% CI will be computed on all estimated percentages. The method for estimating the CIs will be described in the statistical analysis plan.

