10.7. Analysis of Secondary Objectives

The primary analysis of AEs and/or other AEs reported using ADR cards will be descriptive and will be performed on the Safety Set.

For each vaccine dose*, the weekly percentage of subjects reporting AEs and/or other AEs within 7 days post-vaccination period (i.e., the day of vaccination and the following 6 days) using ADR cards will be estimated by MedDRA Preferred Term, overall and by country, as follows:

- The denominator will be the number of subjects *from the Safety Set* vaccinated with GSK's quadrivalent seasonal influenza vaccine during the week of interest (ISO weeks 40 to 52), in a given country or for all countries.
- The numerator will be the number of subjects from the denominator who reported the AE on the ADR card within 7 days following vaccination.

In addition, for each vaccine dose*, the weekly and cumulative percentages of subjects reporting AEs and/or other AEs within 7 days post-vaccination period using ADR cards, according to MedDRA Primary System Organ Class classification, will be estimated in each country and overall, by age strata (6 months to 17 years; 18 to 65 years; >65 years) and risk status (at risk/not at risk).

* Note that a second dose of GSK's quadrivalent seasonal influenza vaccine is planned to be administered only to children aged <9 years who have not previously been vaccinated against influenza in preceding seasons.

95% CI will be computed on all estimated percentages. The method for estimating the CIs will be described in the statistical analysis plan.

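### Interim weekly AE percentages can read falsely low in the newest weeks, because unreturned cards may count as AE-free and section 10.10.2 lists no return rate or returned-card figure

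*Protocol*

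**What the plan says.** Section 10.4 of the protocol has one safety rule: "Subjects who did not report an adverse event will be considered as subjects who did not experience adverse event". Section 10.3.3 defines the Safety Set as "all subjects from the Exposed Set who received the ADR card", whether or not the card came back. Section 10.6 then says: "The primary analysis of AEs and/or other AEs reported using ADR cards will be descriptive and will be performed on the Safety Set". Section 10.7 uses the same set for the weekly percentages, and in both sections "The numerator will be the number of subjects from the denominator who reported the AE on the ADR card within 7 days following vaccination". A subject whose card is missing is therefore in the denominator and cannot be in the numerator.

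The protocol can tell a missing card from a report of no event. Section 4.1 says of the card that "Subjects will also have the possibility to indicate that no AE occurred". Section 9.2 says that a subject who "has not returned the completed ADR card will be considered a withdrawal from the study". Section 10.3.4 defines a Solicited Safety Set of subjects who returned the card.

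For the protocol's analyses in general, 10.5 tabulates the size of each analysis set by ISO week and country. Section 10.8 tabulates the return percentage by centre, by country and overall, and repeats the AE analysis on the Solicited Safety Set.

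Section 10.10.2 gives the interim analyses the purpose of following the trend of AE reporting as safety monitoring. It lists three outputs: numbers vaccinated per ISO week, demographics, and the weekly AE percentage by Preferred Term with a 95% CI. It names no analysis set. On timing, section 4 says that "Subjects will have up to 14 days post vaccination to return their ADR card".

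**The concern.** A card that has not been returned carries no information on whether an AE occurred. Counting it as AE-free moves the percentage towards reassurance, and a larger sample does not remove the shift. In the final analysis a reader can see this, because the return rate and the returned-card analysis are both planned. At an interim analysis, nothing on the 10.10.2 list would show it.

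The newest weeks are the most exposed, because many of their cards may still be outstanding when the data are cut. They are also where a new rise would first appear, and the study's rationale is rapid detection of an increase in expected reactions. A drop in the weekly percentage could reflect late cards, and a real rise could be masked by them.

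**Working it through.** **Inputs.** From the protocol: 75 subjects per week over all countries, true AE percentages up to 10%, and exact Clopper-Pearson limits (10.2, Tables 4 and 5); card return up to 14 days after vaccination (section 4); Visit 2 at Day 8, with 7 to 14 days allowed after Visit 1 (Table 3). Assumed: the return rate r, because none is stated; return unrelated to AEs unless noted; a true 20% as an example of a doubling; an interim data cut at the end of an ISO week, with no lag.

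**The plan's own figures.** For n = 75 and p = 10%, RSE = sqrt((1 − p)/(np)) = sqrt(0.9/7.5) = 34.6%, and the exact CI for 7.5/75 is 4.27 to 19.12%. Both match Table 4, which in effect assumes that every card comes back (r = 100%).

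**Effect of missing cards.** With return rate r among subjects with the AE, the expected Safety Set percentage is p × r. If return does not depend on AEs, the expected returned-card percentage is p.

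**Which weeks are incomplete.** At a cut at the end of an ISO week:
- Subjects vaccinated in the last week are 0 to 6 days past vaccination. None has reached Day 8.
- Subjects vaccinated in the week before are 7 to 13 days past vaccination. None has reached the 14-day limit.

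**Newest week, no cards in.** The Safety Set figure is 0/75, with upper limit 1 − 0.025^(1/75) = 4.80%, as in the first row of Table 5. This interval excludes a true 5% or 10%.

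**A masked doubling, n = 75 per week.**

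| Week | True % | Cards in | Safety Set | Returned cards |
|---|---|---|---|---|
| Earlier | 10 | 80% | 75 × 0.10 × 0.80 = 6; 6/75 = 8.0% (2.99–16.60) | 6/60 = 10% |
| Recent | 20 | 40% | 75 × 0.20 × 0.40 = 6; 6/75 = 8.0% (2.99–16.60) | 6/30 = 20% (7.71–38.57) |

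The Safety Set series is flat, while the returned-card series doubles.

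**How much return has to fall at weekly size.** Coverage of a true 10% by the weekly Safety Set CI, with counts Bin(75, 0.10 × r):

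| r | 100% | 90% | 80% | 70% | 50% | 40% |
|---|---|---|---|---|---|---|
| Coverage | 96.8% | 96.3% | 94.3% | 90.3% | 73.0% | 58.1% |

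For a true 1%, coverage is at least 99.3% at all these rates. Moderate non-return hardly matters in a single week. Weeks with many cards outstanding do.

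**If return depends on AEs.** Take a true 10%, with return of 95% among subjects with the AE and 78% among the others. The Safety Set gives 0.10 × 0.95 = 9.5%. Returned cards give 0.095/(0.095 + 0.90 × 0.78) = 0.095/0.797 = 11.9%. Here the Safety Set figure is the closer of the two.

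**The case against.** The strongest reply is that the study estimates reporting, not occurrence. The objectives in section 3 and the analyses in 10.6 and 10.7 refer to subjects reporting events, and the endpoint in 10.1.1 covers events "i.e., the day of vaccination and the following 6 days) reported using ADR cards, according to MedDRA classification". For that quantity the Safety Set percentage and its interval are correct. The 10.4 sentence also changes no Safety Set number, because 10.6 and 10.7 already fix numerator and denominator. This stands, and it makes the 10.4 part of the point one of wording.

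A reader might go further and infer that the primary analysis is invalid. With n = 1000, a true 10% and an assumed 80% return, the Safety Set CI covers the true percentage only 42.4% of the time. The documents do not support that inference. The 42.4% is coverage of occurrence, which is not the stated objective. It also belongs to the whole-study analysis, where 10.5 and 10.8 already supply set counts by week, return rates and the Solicited Safety Set results.

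The second reply is that 10.10.2 fixes neither the interim analysis set nor the data cut, and that both may be settled in a SAP that is not shown. A lagged cut, or use of returned cards, would be compatible with the text, and a week of zeros for every Preferred Term would be noticed. This stands as a limit: the Safety Set at the interims is inferred from 10.7, which defines the same weekly percentage. It does not remove the point. The protocol itself lists the interim outputs, and a partly returned week showing 8.0% would not stand out as a week of zeros would.

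**Conclusion.** The point holds in a narrow form and is worth fixing. Section 10.4 equates not reporting with not experiencing, and the Safety Set percentage understates occurrence whenever return among subjects with the AE is below 100%. The final analysis already gives readers what they need to see this. The interim list does not.

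If 10.7 is applied at the interims without a lagged cut, the two newest weeks are open to understatement, up to 0/75 when no cards are in, and a doubling from 10% to 20% can appear as a constant 8.0%. The size rests on assumed return rates and on the chosen pair of 80% and 40%. At 80% return a single week of 75 is barely affected (coverage of a true 10% is 94.3%, against 96.8% at full return). The effect becomes clear when about half or more of the cards are outstanding (73.0% at 50%, 58.1% at 40%).

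It should not be inferred that the interim analyses will certainly be misread, since the set and the cut are not fixed, or that returned cards give an unbiased answer.

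**What to change.** 1. In 10.10.2, add for each ISO week, overall and by country, the number and percentage of cards returned and the Solicited Safety Set percentage beside the Safety Set percentage. Flag every week in which the 14-day return period is still open for some subjects.
2. In 10.4, limit the statement about not experiencing an AE to subjects who returned the card for that dose, or state that the Safety Set figure is a percentage reporting among card recipients.

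The primary analysis set does not change and no new data are needed. The cost is a few table columns and a footnote. The returned-card figure is less precise: in the weekly example its interval is 7.71–38.57% on 30 cards, against 2.99–16.60% on 75 subjects. By country, with 25 subjects per week (Table 4), 40% return would leave 10 cards. At n = 1000 with a true 10% and 80% return, the RSE is sqrt(0.9/(0.1 × 800)) = 10.6%, against the 9.5% in Table 4. The returned-card figure also overstates occurrence if subjects with AEs return cards more often, so the two percentages and the return rate should be shown together, with neither percentage presented as unbiased.

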10.5. Analysis of Demographics

The number of subjects included in each analysis set will be tabulated by ISO week (expected ISO weeks 40 to 52), overall and by country.

Demographic characteristics (age at study vaccination in years, gender, race) and risk status will be summarised overall and by country using descriptive statistics for each analysis set:

- Frequency tables will be generated for categorical variables such as gender.
- Mean, standard deviation, median, minimum and maximum will be provided for continuous data such as age.

10.6. Analysis of Primary Objective

The primary analysis of AEs and/or other AEs reported using ADR cards will be descriptive and will be performed on the Safety Set.

For each vaccine dose*, the cumulative percentage of subjects reporting AEs and/or other AEs within 7 days post-vaccination period (i.e., the day of vaccination and the following 6 days) using ADR cards from study start up to each study week (ISO weeks 40 to 52) will be estimated by MedDRA Preferred Term, overall and by country, as follows:

- The denominator will be the number of subjects *from the Safety Set* vaccinated with GSK's quadrivalent seasonal influenza vaccine at any point from study start (i.e., 01 October 2018) up to the end of the week of interest, in a given country or for all countries.
- The numerator will be the number of subjects from the denominator who reported the AE on the ADR card within 7 days following vaccination.

* Note that a second dose of GSK's quadrivalent seasonal influenza vaccine is planned to be administered only to children aged <9 years who have not previously been vaccinated against influenza in preceding seasons.

95% CI will be computed on all estimated percentages. The method for estimating the CIs will be described in the statistical analysis plan.

10.7. Analysis of Secondary Objectives

The primary analysis of AEs and/or other AEs reported using ADR cards will be descriptive and will be performed on the Safety Set.

For each vaccine dose*, the weekly percentage of subjects reporting AEs and/or other AEs within 7 days post-vaccination period (i.e., the day of vaccination and the following 6 days) using ADR cards will be estimated by MedDRA Preferred Term, overall and by country, as follows:

- The denominator will be the number of subjects *from the Safety Set* vaccinated with GSK's quadrivalent seasonal influenza vaccine during the week of interest (ISO weeks 40 to 52), in a given country or for all countries.
- The numerator will be the number of subjects from the denominator who reported the AE on the ADR card within 7 days following vaccination.

In addition, for each vaccine dose*, the weekly and cumulative percentages of subjects reporting AEs and/or other AEs within 7 days post-vaccination period using ADR cards, according to MedDRA Primary System Organ Class classification, will be estimated in each country and overall, by age strata (6 months to 17 years; 18 to 65 years; >65 years) and risk status (at risk/not at risk).

* Note that a second dose of GSK's quadrivalent seasonal influenza vaccine is planned to be administered only to children aged <9 years who have not previously been vaccinated against influenza in preceding seasons.

95% CI will be computed on all estimated percentages. The method for estimating the CIs will be described in the statistical analysis plan.

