2.1. Risk Assessment

Important Potential Risks	Data/Rationale for Risk	Mitigation Strategy
Anaphylaxis	Anaphylaxis can occur at any age, with the highest age-specific rates observed in the 0-19 year group (70 cases per 100,000 person-years). Anaphylaxis following immunisation is serious but rare; the estimated incidences are in the range of 1-10 per 1 million doses distributed depending on the vaccine distributed [Ruggeberg, 2007].	The investigator/prescribers are advised of possible anaphylaxis following GSK's quadrivalent seasonal influenza vaccine administration by information included in product labels.

Important Potential Risks	Data/Rationale for Risk	Mitigation Strategy
Febrile seizure	
In April 2010, there was a reported increase in febrile convulsion following influenza vaccination in young children in Western Australia. Following extensive investigations into this safety issue, epidemiological analyses determined that administration of the 2010 seasonal influenza vaccines, Fluvax® and Fluvax Junior® (manufactured by Bio CSL), was associated with an increased risk of febrile convulsions, however, the risk has not been confirmed for other influenza vaccines, including GSK's quadrivalent seasonal influenza vaccine.
	
As with other vaccines, vaccination with GSK's quadrivalent seasonal influenza vaccine should be postponed in subjects suffering from an acute febrile illness; fever is also listed as an adverse reaction.

Guillain-Barré syndrome (GBS)	
A few cases of GBS have been reported to GSK. Most published studies investigating GBS suggest incidence estimates between 0.84 and 1.91 per 100,000 persons per year. To date, a total of 29 published studies investigating GBS have been carried out in ten European countries. The majority of studies (21/29) provided an incidence estimate that fell between 1.0 and 2.0 per 100,000 persons per year. [McGrogan, 2009].
	
None: GBS is listed as rare adverse reaction in the label. There is no known prevention for GBS.

Bell's palsy	
The annual incidence of Bell's palsy is 15 to 30 per 100,000 people. The peak incidence occurs between the second and fourth decades (15 to 45 years). 10% of patients experience one or more recurrences [Greco, 2012]. Bell's palsy has been reported in people who had intranasal influenza vaccine. A link between Bell's palsy and seasonal influenza vaccine that are given by intramuscular injection has not been established.
	
None

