3.2. Secondary Objectives

- To estimate, in each country and overall, the weekly percentages of subjects reporting AEs and/or other AEs within 7 days following vaccination with GSK's quadrivalent seasonal influenza vaccine using ADR cards, overall, by age strata (6 months to 17 years; 18 to 65 years; >65 years), and risk status (at risk/not at risk).
- To estimate, in each country and overall, the cumulative percentages of subjects reporting AEs and/or other AEs within 7 days following vaccination with GSK's quadrivalent seasonal influenza vaccine using ADR cards, by age strata (6 months to 17 years; 18 to 65 years; >65 years), and risk status (at risk/not at risk).

Refer to Section 10.1.2 for the definition of the secondary endpoints.

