10.10.2. Statistical considerations for interim analyses

The interim analyses will be generated to evaluate the trend of reporting of AEs (i.e. safety monitoring) and will be performed on data which are cleaned as much as possible.

The following analyses will be performed for each interim analysis, overall and by country:

- The number of subjects vaccinated with GSK's quadrivalent seasonal influenza vaccine during each ISO week will be tabulated overall, by age strata and risk status.
- Demographic characteristics (age at study vaccination in years, gender, race) will be summarised using descriptive statistics.
- The weekly percentage of subjects reporting AEs and/or other AEs within 7 days post-vaccination period (i.e., the day of vaccination and the following 6 days) using ADR cards will be estimated by MedDRA Preferred Term, with 95% CI.

Since there is no hypothesis testing, no adjustment of type I error will be needed.

No study report will be written for the interim analyses.

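### Results by age stratum and risk status are planned at System Organ Class level, so no dose 1 table shows a single pre-defined AEI within a stratum

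*Protocol*

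**What the plan says.** The second of the secondary objectives in Protocol section 3.2 asks for the "cumulative percentages of subjects reporting AEs and/or other AEs within 7 days following vaccination", split "by age strata (6 months to 17 years; 18 to 65 years; >65 years), and risk status (at risk/not at risk"). Neither this objective nor the endpoints in 10.1.2 name a level of the MedDRA hierarchy. The level is set in the analysis sections:

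- Section 10.6, primary cumulative percentages: "will be estimated by MedDRA Preferred Term, overall and by country, as follows".
- Section 10.7, weekly percentages: "using ADR cards will be estimated by MedDRA Preferred Term, overall and by country, as follows".
- Section 10.7, additional paragraph on weekly and cumulative percentages by stratum: "according to MedDRA Primary System Organ Class classification, will be estimated in each country and overall, by age strata" and risk status.
- Section 10.10.2, interim weekly percentages: "using ADR cards will be estimated by MedDRA Preferred Term, with 95% CI", overall and by country. At the interims only the number vaccinated is split by age and risk, being the count that "during each ISO week will be tabulated overall, by age strata and risk status".

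Section 10.8 repeats the AE analysis on the Solicited Safety Set and adds no Preferred Term split by stratum. Appendix B defines each pre-defined AEI by a MedDRA Preferred Term, fever for example as Pyrexia.

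**The concern.** The introduction gives the purpose of enhanced surveillance as rapid detection of an increase in expected local, systemic or allergic reactions. These are single reactions, and Appendix B codes them that way. In a class-level table a subject counts once for any event in the class. A subject with a new fever who would have reported another event of that class anyway adds nothing to the count, and the other events raise the baseline against which the change is read. The age and risk strata are where the objectives ask for a closer look, yet they are the only split of the AE results for which 10.7 moves to the coarser level. At stake is the ability to see, from the planned dose 1 tables, a rise in one expected reaction that is confined to children, to subjects over 65 or to those at risk.

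**Working it through.** **Plan's own figures.** The point disputes no stated figure. As a check on Table 4, n = 333 and a true percentage of 1% give P(at least one) = 1 − 0.99^333 = 96.5% and relative standard error = √(0.99 / (333 × 0.01)) = 54.5%, both as printed.

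**What the planned dose 1 tables show for one AEI.**

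- Preferred Term, all subjects: planned (10.6, 10.7).
- Preferred Term, by country: planned (10.6, 10.7).
- Preferred Term, by age stratum or risk status: not planned in any section.
- System Organ Class, by age stratum and risk status: planned (10.7).

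**Dilution at class level.** Let f be the percentage of children with fever and s the percentage with any other event of the same class. Assuming independence, the class percentage is 1 − (1 − s)(1 − f). The protocol gives neither f nor s. Assume f rises from 3% to 9%, a ratio of 3.0 at Preferred Term level.

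- s = 20%: 1 − 0.80 × 0.97 = 22.4%, then 1 − 0.80 × 0.91 = 27.2%; ratio 1.21.
- s = 50%: 1 − 0.50 × 0.97 = 51.5%, then 1 − 0.50 × 0.91 = 54.5%; ratio 1.06.

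**What Spain's Preferred Term table would show.** By section 5.2 only Spain enrols children, and it targets ages 6 months to 65 years. Let c be the child share in Spain and assume adult fever stays at 2%. The Spanish percentage is c × f + (1 − c) × 2%.

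- c = 30%: 0.9 + 1.4 = 2.3%, then 2.7 + 1.4 = 4.1%; ratio 1.8.
- c = 70%: 2.1 + 0.6 = 2.7%, then 6.3 + 0.6 = 6.9%; ratio 2.6.

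**Against sampling error.** This second illustration uses other assumed rates: fever in 200 children doubling from 5% to 10%. The yardstick is the exact binomial chance that the lower 95% Clopper-Pearson limit lies above the old percentage, taken as fixed. The plan contains no such test.

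- Preferred Term: at least 17 cases are needed; chance 79%.
- Class, s = 20% (24.0% to 28.0%): at least 61 are needed; chance 24%.
- Class, s = 50% (52.5% to 55.0%): at least 120 are needed; chance 9%.

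With 100 children the chances are 42% at Preferred Term level and 6.5% to 11% at class level.

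**Size of the strata.** The protocol gives no enrolment by age. With 333 subjects in Spain (Table 4) and c from 30% to 70%, the final child stratum is 0.3 × 333 ≈ 100 to 0.7 × 333 ≈ 233. The plan already reports Preferred Terms by country and week, where Table 4 assumes 25 subjects.

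**The case against.** A reader might infer that no output shows any single AEI in children. That goes too far. The Preferred Term analyses are planned for each dose, and dose 2 is given only to previously unvaccinated children under 9, so those tables are wholly paediatric. Spain's Preferred Term table is a partial substitute for dose 1 and keeps much of the signal in the illustration.

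A reader might also link the point to the event in section 2.1, where "there was a reported increase in febrile convulsion following influenza vaccination in young children in Western Australia", and conclude that such a signal would be lost. The documents do not support this. The same section says the risk has not been confirmed for this vaccine. Febrile convulsion has its own Preferred Term in Appendix B, so it keeps its own line overall and in Spain. Section 8.1.2 lists convulsions without hospitalisation among examples of serious events, and 10.8 has vaccine-related serious events described in detail.

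The size of the dilution is not known from the documents. The fever rates, s, independence, adult fever and the child share are all assumed. The protocol does not list which terms share a class with Pyrexia, and the group headings in Appendix B are not stated to be System Organ Classes.

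Class level for subgroups is also a defensible way to limit sparse output. Appendix B has 31 Preferred Terms, and crossing them with age, risk status, country, dose and 13 weeks gives a very large number of cells in about 1000 subjects. This stands for the weekly stratified tables. It is weaker for the cumulative ones, given that country-by-week tables are already at Preferred Term level, although cumulative strata will be small in the first weeks too.

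Finally, 10.7 does not forbid Preferred Term rows, and an SAP not shown here could add them. But 10.7 defers only the confidence interval method to the SAP, and it names the class level in direct contrast to the Preferred Term wording just before it. As written, the level is a stated choice.

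**Conclusion.** The point holds as a gap in the planned outputs. No dose 1 table shows a single pre-defined AEI separately in children, in subjects over 65 or by risk status. For children, the dose 2 tables and Spain's table close part of it. For risk status no planned Preferred Term table gives any separation. For subjects over 65 the nearest is Germany's table, which by section 5.2 mixes them with subjects from about 50 upwards.

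A rise in one reaction within a stratum is diluted, not fully hidden: a very large rise, or one in a class with few other reports, could still show. Under the assumptions above, a threefold rise in fever in children appears as 1.06 to 1.21 at class level and about 1.8 to 2.6 in Spain's Preferred Term table. These figures illustrate the mechanism and are not estimates for this vaccine. The point is a cheap improvement to a descriptive plan. It is not an error in a stated figure, and because sections 3.2 and 10.1.2 set no MedDRA level, it is not a contradiction of the objectives either.

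**What to change.** In section 10.7, add for each dose the cumulative percentage with 95% CI by Preferred Term, at least for the pre-defined AEIs of Appendix B, by age stratum and by risk status, overall and by country. Keep System Organ Class for the weekly stratified tables, where cells are smallest.

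The data are already coded to Preferred Term, and since all analyses are descriptive, neither the sample size nor the conduct of the study changes. The cost is one more set of descriptive tables. Some cells will be small, particularly in the first weeks and within country, and those intervals will be wide.
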